Correlation and Comparison of the HepQuant® Disease
Severity Index (DSI) With Hepatic Venous Pressure
Gradient (HVPG)

NCT02523196

Protocol Version: August 11, 2015

Protocol #: 15-0520

Project Title: Correlation and comparison of the HepQuant® Disease Severity Index (DSI) with Hepatic Venous Pressure Gradient (HVPG)

Principal Investigator: [name].

Version Date: August 11th, 2015

I. Hypotheses and Specific Aims:

Hypothesis

The HepQuant® (HQ)-SHUNT test is an appropriate alternative to Hepatic Venous Pressure Gradient (HVPG) testing.

Specific Aims

HQ-SHUNT is safe, simple to administer, noninvasive, cost-effective, and well tolerated by patients. In order to prove that the HQ-SHUNT test is an appropriate alternative to measurement of HVPG we will conduct a head-to-head comparison of HQ-SHUNT to HVPG. In this study, 100 consecutive patients with various etiologies of liver disease who have undergone technically successful HVPG testing will subsequently undergo HQ-SHUNT testing.

Primary Aim 1: Create the ROC curve of the Disease Severity Index (DSI) from HQ-SHUNT for defining patients with (HVPG ≥ 6 mmHg) and without (HVPG < 6 mmHg) portal hypertension. From the ROC, define the optimal cutoff of DSI and the sensitivity, specificity, and positive and negative predictive values.

Primary Aim 2: In patients with portal hypertension (HVPG ≥ 6 mmHg), define the optimal relationship of DSI to HVPG.

Exploratory Aims

Approximately 90% of patients undergoing HVPG will have liver biopsy performed as part of the procedure. In addition, most of the patients undergoing HVPG will have undergone or will undergo upper gastrointestinal endoscopy (EGD) to evaluate for varices and variceal treatment. This allows a head-to-head comparison of DSI from HQ-SHUNT with HVPG in identifying patients with cirrhosis and patients with varices. Finally, we will also compare the tolerability of both HVPG and HQ-SHUNT, since tolerability of procedures is critical for patient acceptance and the ability to perform serial testing.

Exploratory Aim 1: Compare the cutoffs of DSI 16.5 and HVPG 6 mmHg in identifying patients with cirrhosis.

Exploratory Aim 2: Compare the cutoffs of DSI 20 and HVPG 10 mm Hg in identifying patients with varices.

Exploratory Aim 3: Survey patients on their experience of having both HQ-SHUNT and HVPG procedures.

II. Background and Significance:

The Clinical Problem in Liver Disease Assessment and Liver Disease Drug Development

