Both HVPG and HQ-SHUNT results correlate with fibrosis stage, prevalence of cirrhosis, and the prevalence and size of varices [7], [8], [9]. DSI appears to have a better and more linear correlation with fibrosis, and more sensitivity at lower fibrosis stages than HVPG (Fig. 3). However all the results summarized above were from separate studies and the two methods have never before been compared in a head-to-head fashion.

IV. Research Methods

A. Outcome Measure(s):

The following outcome measures will be assessed for each Specific Aim:

Primary Aim 1. Two measurements will be compared, HVPG and DSI. The HVPG test results will define the patients with portal hypertension (HVPG ≥ 6 mmHg). DSI will be determined from the HepQuant (HQ)-SHUNT test and the DSI cutoff for portal hypertension will be defined from ROC analysis.

Primary Aim 2. Two measurements will be compared, HVPG and DSI. The relationship between these measurements, in the patients with portal hypertension, will be analyzed by linear and nonlinear regression.

Exploratory Aims:

Exploratory Aim 1. The outcome measure is cirrhotic fibrosis score on liver biopsy. Prevalence of cirrhosis will be determined for cutoffs of DSI 20 and HVPG 6 mmHg.

Exploratory Aim 2. The outcome measure is medium to large varices at EGD. Prevalence of varices will be determined for cutoffs of DSI 20 and HVPG 10 mmHg.

Exploratory Aim 3. The outcome measure is patient tolerability for testing procedures defined by the Patient Survey.

B. Description of Population to be Enrolled:

Inclusion Criteria

- Liver disease patient scheduled to have an Hepatic Venous Pressure Gradient (HVPG) procedure
- At time of enrollment, being between the ages of 18 and 75

Exclusion Criteria

- Concomitant treatment with both a beta blocker and an ACE inhibitor
- Concurrent hepatic malignancy. Patients with a history of treated HCC can be included if there is no evidence of recurrent disease at the time of this study.
- Unstable angina or history of myocardial infarction or congestive heart failure within 6 months prior to enrollment into this study
- Renal insufficiency with chronic kidney disease stage 4 or 5 (GFR < 30 mL/min/1.73m²)
- Crohn's disease or any active intestinal inflammatory condition
- Having had an ileal resection
- Diabetic Gastroparesis
- Pregnancy or intent to become pregnant. Urine pregnancy tests will be performed prior to HQ SHUNT testing.
- Inability to consent for one's self

Stopping Criteria

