- Decision by subject to withdraw from study for any reason
- Development of any of the above-mentioned exclusion criteria (being diagnosed with a hepatic malignancy, becoming or intending to become pregnant, clinical decompensation, development of unstable coronary disease, congestive heart failure or renal insufficiency with GFR < 30mL/min/1.73m²)
- Adverse reaction to test compounds

C. Study Design and Research Methods

Patient Selection

The HVPG procedure costs ~\$8500 and is currently ordered on a case-by-case basis as part of the standard of care (SOC) for liver disease. Patients already scheduled to have an HVPG measurement will be recruited to participate in this study of "Correlation and Comparison of HQ-SHUNT with HVPG". The HVPG procedure is quite uncomfortable, requires sedation and commitment of an entire day. Therefore, patients will not undergo HQ-SHUNT testing on the day of their HVPG, but rather within a window of ±60 days of their HVPG. Liver disease progresses slowly over years so that HQ-SHUNT® and HVPG results will represent the patient's current status. Patients will be censored in the analysis if clinical decompensation occurs between the HQ-SHUNT and HVPG tests.

We will enroll 110 patients into the study. Over 90% of all HVPG tests performed by UCH Radiology are ordered through the Hepatology clinic at UCH. Patients and care providers in the Hepatology clinic will be made aware of the "Correlation and Comparison of HQ-SHUNT with HVPG" study via direct communications. Patients may be enrolled within 60days following the performance of the HVPG procedure. HQ-SHUNT tests will only be performed in the patients who had a technically successful HVPG test as determined by the radiologist performing the procedure. All HQ-SHUNT tests will be performed within the 60 days following the HVPG test. HQ-SHUNT will only be performed in patients whose clinical status is stable and who have not had any major intervening procedures such TIPS or surgical shunt. Elective EGD and banding of varices, in an otherwise clinically stable patient is an allowable intervention.

PROCEDURES AND METHODS

HVPG

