Primary Aim 1: Assuming that there are 50 patients with and 50 patients without portal hypertension in the study, a sample size of 50 from the portal hypertension group and 50 from the no portal hypertension group achieve 80% power to detect a difference of 0.14 between the area under the ROC curve (AUC) for DSI under the null hypothesis of 0.65 and an AUC under the alternative hypothesis of 0.79 using a two-sided z-test at a significance level of 0.05. The data are continuous responses. The AUC is computed between false positive rates of 0 and 1. The ratio of the standard deviation of the responses in the negative group to the standard deviation of the responses in the positive group is 1.

The following table shows the range of AUC's that can be detected based on alternative scenarios for the null hypothesis AUC using HQ-SHUNT:

Numeric Results for Testing AUC0 = AUC1 with Continuous Data

Test Type = Two-Sided. False positive rate1 = 0.000. False positive rate2 = 1.000. B (ratio of SDs) = 1.000.

Power	N+	N-	AUC0	AUC1	Difference	Alpha	Beta
0.80000	50	50	0.6500	0.7945	0.1445	0.05000	0.20000
0.80000	50	50	0.6600	0.8029	0.1429	0.05000	0.20000
0.80000	50	50	0.6700	0.8113	0.1413	0.05000	0.20000
0.80000	50	50	0.6800	0.8196	0.1396	0.05000	0.20000
0.80000	50	50	0.6900	0.8278	0.1378	0.05000	0.20000
0.80000	50	50	0.7000	0.8359	0.1359	0.05000	0.20000
0.80000	50	50	0.7100	0.8439	0.1339	0.05000	0.20000
0.80000	50	50	0.7200	0.8518	0.1318	0.05000	0.20000
0.80000	50	50	0.7300	0.8597	0.1297	0.05000	0.20000
0.80000	50	50	0.7400	0.8674	0.1274	0.05000	0.20000
0.80000	50	50	0.7500	0.8751	0.1251	0.05000	0.20000
0.80000	50	50	0.7600	0.8826	0.1226	0.05000	0.20000
0.80000	50	50	0.7700	0.8901	0.1201	0.05000	0.20000
0.80000	50	50	0.7800	0.8975	0.1175	0.05000	0.20000
0.80000	50	50	0.7900	0.9047	0.1147	0.05000	0.20000
0.80000	50	50	0.8000	0.9119	0.1119	0.05000	0.20000

Primary Aim 2: Assuming that there are 50 patients with portal hypertension, the following table shows the 95% confidence intervals around correlations ranging from 0.4 to 0.8 with a sample size of 50 patients with portal hypertension:

Numeric Results for Two-Sided Confidence Intervals for One Correlation

Confidence Level	Sample Size (N)	Actual Correlation	Width	Lower Limit	Upper Limit	Width if R = 0.0
0.950	50	0.473	0.400	0.137	0.610	0.557
0.950	50	0.426	0.500	0.257	0.683	0.557
0.950	50	0.367	0.600	0.386	0.753	0.557
0.950	50	0.295	0.700	0.524	0.819	0.557
0.950	50	0.211	0.800	0.671	0.882	0.557

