Correlation (R) is the assumed sample correlation.
Width if R = 0.0 is the maximum width for a confidence interval with sample size N.

For the linear regression analysis, a sample size of 50 achieves 80% power to detect a change in slope from 0 under the null hypothesis to 0.50 under the alternative hypothesis when the standard deviation of DSI is 3, the standard deviation of HVPG is 4.00, and the two-sided significance level is 0.05.

General Statistical Analysis

Primary Aim 1. It is expected that both HQ-SHUNT results and HVPG measurements will reflect the extent of liver disease. Higher pressures will in general be associated with lower Systemic HFR and Portal HFR, and with higher SHUNT and DSI. The performance of DSI to identify patients with portal hypertension (HVPG ≥ 6 mmHg) will be determined by ROC analysis. Optimal DSI cutoff, sensitivity, specificity, PPV, and NPV will be defined.

Primary Aim 2. We will develop models of the relationships of HQ-SHUNT test results to the HVPG test results based on correlations. We expect there to be a linear relationship for HVPG pressures between 6 and 25 mmHg (i.e. in patients with portal hypertension) and will assess the correlation (with 95% confidence intervals) for HVPG vs. DSI in the 50 patients expected to have HVPG pressures ≥ 6 mmHg. Linear regression will be used to assess the relationship between these variables, taking other covariates into account, and R^2 values will be reported.

Exploratory Aims:

Exploratory Aim 1. It is expected that both HQ-SHUNT results and HVPG measurements will, in general, reflect the extent of liver disease, as measured by the liver fibrosis stage and by the D'Amico cirrhosis stage. Regression models will be developed of the relationships of HQ-SHUNT test results to fibrosis stage and to cirrhosis stage. Likewise regression models will be developed of the relationship of HVPG portal pressure to fibrosis stage and to cirrhosis stage. It is expected that correlations will be found similar to those shown in Fig 3, but now demonstrated in the same patient population.

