Exploratory Aim 2. HQ-SHUNT test results will be compared to HVPG test results at identifying patients with all sizes of varices, as well as at identifying just those patients with medium to large varices that require therapeutic intervention, usually banding. These comparisons will be made using ROC curves and their associated c-statistics. The optimum diagnostic cutoffs of each test will be determined from the ROC curves by the Youden index (J statistic). The sensitivity, specificity, PPV, and NPV of each test will be compared at their respective optimum diagnostic cutoffs.

Exploratory Aim 3. For each procedure, HVPG and HQ-SHUNT testing, the patients will report their pain, discomfort, inconvenience, overall experience, and willingness to undergo repeat testing, each on a scale of 1 to 10. The numerical scores of each question will be compared between the HVPG and HQ-SHUNT testing, in terms of mean score, standard deviation, and statistical significance (t-test).

G. Summarize Knowledge to be Gained:

Overall this study will demonstrate whether The HQ-SHUNT test results can generate physiological information on liver disease patients that is as good, or better, than HPVG pressure measurements. A close correlation between HQ-SHUNT test results and HPVG pressure measurements would allow the safer, less invasive, lower cost HQ-SHUNT test to replace HVPG in patient assessment and in clinical trials of new liver disease therapies and therapeutic agents. However the HQ-SHUNT test reports on the systemic clearance, portal clearance, and portal-systemic shunt and provides a more comprehensive picture of the portal circulation than just the portal pressure. For example, the presence of extensive or large collaterals, such as a spleno-renal collateral, should relieve portal pressure, reduce varices, and reduce the HVPG; while, in contrast, HQ-SHUNT would reveal an increase in SHUNT and DSI. In terms of disease severity, HVPG would be falsely low, while HQ-SHUNT would report accurately.

Varices are clinically very serious because they require intervention to prevent internal bleeding. An HVPG > 10 mm HG has been associated with a risk of varices. A DSI > 20 similarly indicates a risk of large varices, ROC c-statistic 0.82, sensitivity 86%, specificity 65%. This study allows a direct comparison in the same patients of the relative ability of HQ-SHUNT and HVPG to identify patients with varices.

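### Section IV.G moves from a close correlation to replacing HVPG, but Primary Aim 2 plans no error in mmHg to show how well DSI recovers an individual HVPG

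*Combined protocol and SAP*

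**What the plan says.** Section I sets Primary Aim 2: "In patients with portal hypertension (HVPG ≥ 6 mmHg), define the optimal relationship of DSI to HVPG". Section IV.A gives the method: "The relationship between these measurements, in the patients with portal hypertension, will be analyzed by linear and nonlinear regression".

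Section IV.F, General Statistical Analysis, says the investigators "will assess the correlation (with 95% confidence intervals) for HVPG vs. DSI in the 50 patients" expected to reach 6 mmHg. It adds: "Linear regression will be used to assess the relationship between these variables, taking other covariates into account, and R^2 values will be reported".

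The sizing for this aim, also in IV.F, has two parts. One is a table of "95% confidence intervals around correlations ranging from 0.4 to 0.8 with a sample size of 50 patients with portal hypertension". The other is a power statement for a regression with 50 patients to "detect a change in slope from 0 under the null hypothesis to 0.50 under the alternative hypothesis", with SDs of 3 for DSI and 4 for HVPG.

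Section IV.G then draws the consequence: "A close correlation between HQ-SHUNT test results and HPVG pressure measurements would allow the safer, less invasive, lower cost HQ-SHUNT test to replace HVPG". The sentence goes on to name both patient assessment and trials of new therapies.

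No section plans a residual SD, a prediction interval or a validation of predicted HVPG. None sets a value of r, of R-squared or of error in mmHg that would count as close.

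**The concern.** A correlation describes how tightly two measurements move together across a group, and it depends on how widely the group is spread. Replacing a test in patient assessment requires something else: that the new result tells the clinician, within a tolerable error, what the old one would have been. DSI and HVPG have different units, so a direct difference between them has no meaning. The relevant quantity is the error when HVPG is predicted from DSI.

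Without that error, and without a limit to hold it against, the report could present a correlation that sounds strong and conclude in favour of replacement, while an individual HVPG remained loosely determined. The powered hypothesis, a slope different from zero, is weaker still: it can be met when DSI removes very little of the spread in HVPG.

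**Working it through.** **Inputs.** From IV.F, Power and Sample size, Primary Aim 2: n = 50, SD of DSI 3, SD of HVPG 4 mmHg, slope 0 against 0.50, two-sided alpha 0.05, power 80%, and tabulated correlations from 0.4 to 0.8. From section II: HVPG thresholds of 6 and 10 mmHg. An acceptable prediction error is not given.

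**Step 1. Reproduce the plan's figures.**
- Slope power, with DSI as predictor and HVPG as response: r = 0.50 × 3/4 = 0.375, so R-squared = 0.14. Noncentrality = √50 × 0.375/√(1 − 0.375²) = 2.86 on 48 df, which gives power 0.800 and matches the plan. With the roles swapped, r = 0.50 × 4/3 = 0.667 and power exceeds 0.999, so HVPG as response is inferred.
- Correlation table: Fisher's z with standard error 1/√47 gives 0.137 to 0.610 at r = 0.4 and 0.671 to 0.882 at r = 0.8, as tabulated.

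**Step 2. Residual SD of HVPG given DSI** = 4 × √(1 − r²). The proportional reduction is 1 − √(1 − r²).

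**Step 3. 95% prediction limits for a new patient at the mean DSI** = t(48) × residual SD × √(1 + 1/50), with t(48) = 2.011. At r = 0.8 this is 2.011 × 2.40 × 1.010 = 4.87. With no DSI, t(49) × 4 × √1.02 = 8.12.

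| r | R-squared | Residual SD (mmHg) | Reduction | 95% limits (mmHg) |
|---|---|---|---|---|
| no DSI | – | 4.00 | – | ±8.1 |
| 0.375 (powered effect) | 0.14 | 3.71 | 7% | ±7.5 |
| 0.4 | 0.16 | 3.67 | 8% | ±7.4 |
| 0.6 | 0.36 | 3.20 | 20% | ±6.5 |
| 0.8 | 0.64 | 2.40 | 40% | ±4.9 |

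**Step 4. How firm these are.**
- Across the plan's own CI for r = 0.8 (0.671 to 0.882), the limits run from ±6.0 to ±3.8 mmHg.
- With 48 df the residual SD has a 95% CI of √(48/chi-square), or 0.834 to 1.249 times its estimate. At r = 0.8 that is 2.00 to 3.00 mmHg.
- If the SD of HVPG were 3 instead of 4 (assumption), the limits would be ±4.9 at r = 0.6, ±3.7 at r = 0.8 and ±6.1 with no DSI. If it were 5 (assumption), they would be ±8.1, ±6.1 and ±10.1.
- At 2 SD from the mean DSI, with SD 4, the limit at r = 0.8 widens only to ±5.1.

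**Step 5. What the other aims cover.** Primary Aim 1 classifies HVPG from DSI at 6 mmHg. Exploratory Aim 2 uses the 10 mmHg cutoff, but it compares both tests against varices. No aim asks how well DSI identifies HVPG at 10 mmHg.

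**The case against.** The strongest reply is that the target is one forward-looking sentence in a summary, not a decision rule. Section II calls this a proof-of-concept study. The text after the quoted sentence argues that DSI should depart from HVPG when collaterals are large, and the exploratory aims judge both tests against cirrhosis and varices. On that view, recovering a value in mmHg is only one meaning of replacement. This lowers the stakes. It does not define close, and the collateral example is itself a reason to quantify the error.

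Three further objections stand and shape the point.
- A reader might infer that the planned R-squared hides what DSI contributes, because it comes from a model with covariates. The documents do not support that: a DSI–HVPG correlation without covariates is planned separately, and its square is the DSI-only R-squared for a straight line. With the SD of HVPG, a residual SD can be derived from it. What remains missing is the planned output in mmHg and a limit to judge it by.
- Cross-validation matters little for one straight line. With an average leverage of 2/50 = 0.04, the leave-one-out residual SD at r = 0.8 is about 2.40/√0.96 = 2.45 mmHg. It matters if several nonlinear forms are compared to find the optimal relationship.
- Limits fitted only where HVPG is at least 6 mmHg are conditional on the result being replaced. In use, nobody would know who belongs to that subset without HVPG. The cut at 6 also strains the normal-residual assumption: the no-DSI range falls below 6 mmHg whenever mean HVPG is under about 6 + 8.1 = 14.1. A fit in all patients is therefore needed.

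**Conclusion.** The point holds for the step from correlation to replacement in individual patients. On the plan's inputs, a study succeeding exactly at its powered effect would narrow the 95% limits for an individual HVPG only from ±8.1 to ±7.5 mmHg. The highest correlation tabulated still leaves ±4.9, wider than the 4 mmHg between the plan's two thresholds. These figures assume linearity, constant variance, normal residuals and an SD of HVPG of 4 mmHg. The documents give no SD for all patients, so the corresponding limits there cannot be computed in advance.

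A reader might go further and infer that DSI cannot replace HVPG, or that the study cannot address its hypothesis. Neither follows. The documents set no acceptable error. The limits also contain HVPG's own measurement error, for which no repeatability figure is given, and any change between the tests, since "All HQ-SHUNT tests will be performed within the 60 days following the HVPG test". Not all of the error belongs to DSI. The planned analyses remain valid for association, and other aims bear on the hypothesis. Group-level use in trials is a separate question that individual prediction limits do not settle. The point is worth acting on, at modest severity.

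**What to change.** 1. For HVPG predicted from DSI alone, report the residual SD with its CI and the 95% prediction limits in mmHg. Do this in the subset with HVPG of at least 6 mmHg and in all patients (about 100). Cross-validate if several nonlinear forms are compared.
2. In all patients, report the sensitivity and specificity of DSI for HVPG at 10 mmHg with 95% CIs, as a secondary output.
3. Reword the section IV.G sentence to claim association rather than replacement, unless the sponsor sets in advance an acceptable error in mmHg and the prediction error meets it.

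The cost is a few extra outputs from data already collected and one sentence of wording. The headline may be less favourable, and a limit set in advance can be missed.

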Previous studies (Fig. 3) suggest that HQ-SHUNT DSI will have a better, more linear correlation with fibrosis (higher r^2), and more sensitivity at lower fibrosis stages than HVPG. Patients with D'Amico cirrhosis stage 1 (no varices), stage 2 (varices), and stages 3-4 (decompensation) had mean HVPG's of 10, 12, and 17 mm Hg [11] while a study of the PSC patients with no varices, varices, or decompensation found mean HQ-SHUNT DSI's of 14, 20, and 35, suggesting that HQ-SHUNT will be comparable to HVPG at early cirrhosis stages. HVPG leveled off and could not distinguish later cirrhosis stages 3-4 [12], but studies of HQ-SHUNT at Baylor University Medical Center, Dallas, found a wide range of DSI's in decompensated patients, up to a DSI of ~ 50 . These results suggest that HQ-SHUNT will be better than HVPG at assessing and differentiating the later clinical stages of cirrhosis.

It is expected that patients will overwhelmingly prefer HQ-SHUNT as having only a minor needle stick, not requiring sedation, and not interfering much with their routine. Patient acceptance is very important when tests must be repeated over several months to follow the efficacy of a new treatment or drug.

In summary, this study could demonstrate whether HQ-SHUNT could be the safer, less invasive, lower cost, superior alternative to HVPG providing greater accuracy and more information over the entire spectrum of disease severity.

H. References:

4. Ripoll C. Hepatic venous pressure gradient and outcomes in cirrhosis. *Journal of clinical gastroenterology*. 2007;41 Suppl 3:S330-5.

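### The planned analyses cannot support the stated conclusion that HQ-SHUNT is as good as or better than HVPG: Primary Aim 1 uses HVPG as the reference, Primary Aim 2 measures only association, and the exploratory comparisons have no paired difference or interval

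*Combined protocol and SAP*

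**What the plan says.** The hypothesis in Section I is modest: "The HepQuant® (HQ)-SHUNT test is an appropriate alternative to Hepatic Venous Pressure Gradient (HVPG) testing". Section IV.G goes further. It says the study will show whether HQ-SHUNT "can generate physiological information on liver disease patients that is as good, or better, than HPVG pressure measurements", and its last sentence adds, in conditional terms, the possibility of a "superior alternative to HVPG providing greater accuracy and more information over the entire spectrum of disease severity".

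The analyses that might support these statements are:

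- **Primary Aim 1** (Section IV.A): "The HVPG test results will define the patients with portal hypertension (HVPG ≥ 6 mmHg"). DSI is then assessed by ROC analysis against that status.
- **Primary Aim 2** (Section IV.F): the investigators "will assess the correlation (with 95% confidence intervals) for HVPG vs. DSI in the 50 patients expected to have HVPG pressures ≥ 6 mmHg", and add a linear regression with covariates.
- **Exploratory Aim 1, cirrhosis.** Section I says the DSI and HVPG cutoffs will be compared. Section IV.A gives the prevalence of cirrhosis at a cutoff of each test. Section IV.F models HQ-SHUNT results against fibrosis and cirrhosis stage, then says "Likewise regression models will be developed of the relationship of HVPG portal pressure to fibrosis stage and to cirrhosis stage".
- **Exploratory Aim 2, varices.** Sections I and IV.A name DSI 20 and HVPG 10 mmHg. Section IV.F compares the tests by ROC curves and c-statistics, and then by sensitivity, specificity, PPV and NPV at each test's own Youden-optimal cutoff.

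The only significance test named for a contrast between the two procedures is the t-test on survey scores in Exploratory Aim 3. That concerns tolerability.

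**The concern.** A claim that one test is as accurate as another, or more accurate, needs both tests measured against a third standard and an estimate of the difference with its uncertainty. The primary aims have no third standard. The exploratory aims have one, but no estimate of the difference is specified.

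As written, two similar c-statistics could be reported as showing that DSI is as good as HVPG, and a numerically higher one as showing that it is better, with nothing in the plan to say how much evidence either statement needs. This matters because Section IV.G goes on to say that a close correlation would let HQ-SHUNT replace HVPG in patient assessment and in trials.

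**Working it through.** **1. The plan's own figures reproduce, but concern other questions.**

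- *Primary Aim 1.* Inputs from Section IV.F: 50 with and 50 without portal hypertension, AUC 0.65 against 0.7945, two-sided alpha 0.05. With the Hanley-McNeil variance the standard errors are 0.0548 (null) and 0.0450 (alternative). Power = Φ[(0.1445 − 1.96 × 0.0548)/0.0450] = 79.5%, against the stated 80%.
- *Primary Aim 2, correlation.* Fisher-z limits for n = 50 match the table for correlations of 0.4 to 0.8; at 0.5 they are 0.257 to 0.683.
- *Primary Aim 2, slope.* Slope 0.50, SD of DSI 3 and SD of HVPG 4 imply r = 0.50 × 3/4 = 0.375. Power by noncentral t is 80.0%.

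These concern one AUC against a fixed value, one correlation and one slope against zero. None concerns a difference in accuracy between DSI and HVPG.

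**2. What each aim can show.**

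| Aim | Reference | Could it show DSI as good or better? |
|---|---|---|
| Primary 1 | HVPG itself | No. HVPG has AUC 1.0 by construction, so DSI can at best tie |
| Primary 2 | None; two measurements related to each other | No. It estimates association only |
| Exploratory 1 | Biopsy, cirrhosis stage | Yes in principle, but no between-test difference is specified |
| Exploratory 2 | EGD | Yes in principle, but no paired difference or interval is specified |

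On Primary Aim 2: even a correlation of 0.8, the highest in the plan's table, leaves 1 − 0.8² = 0.36 of the variance unshared. The correlation does not say which test that remainder belongs to.

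**3. How wide an interval for the difference would be.**

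Half-width = 1.96 × √[2V(1 − r)], where r is the correlation between the two AUC estimates and

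V = [A(1 − A) + (n₁ − 1)(Q₁ − A²) + (n₀ − 1)(Q₂ − A²)]/(n₁n₀), with Q₁ = A/(2 − A) and Q₂ = 2A²/(1 + A).

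From the documents: about 90% of 100 patients biopsied, so about 90. Assumed: both AUCs equal to A, with A from 0.80 to 0.85 (Section IV.G quotes 0.82 for DSI and large varices); r from 0.3 to 0.7; the splits below; and 70 to 90 patients with EGD, 40% of them with varices.

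Example, 45 with and 45 without cirrhosis:

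- A = 0.80: V = (0.16 + 44 × 0.02667 + 44 × 0.07111)/2025 = 0.002204. With r = 0.3, half-width = 1.96 × √(2 × 0.002204 × 0.7) = 0.109.
- A = 0.85: V = 0.001697. With r = 0.7, half-width = 1.96 × √(2 × 0.001697 × 0.3) = 0.063.

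| Target | With / without | 95% half-width |
|---|---|---|
| Cirrhosis | 45 / 45 | 0.063 to 0.109 |
| Cirrhosis | 30 / 60 | 0.072 to 0.124 |
| Varices | 28 / 42 | 0.076 to 0.132 |
| Varices | 36 / 54 | 0.067 to 0.116 |

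**4. Scale of a formal comparison.** Assume N = 100, 20% to 50% reference-positive, and r from 0.3 to 0.7. A difference of 0.77 against 0.71 (the outcome c-statistics in Section III, from separate studies, borrowed for scale only) would be detected with 11% to 34% power. With both AUCs at 0.82, non-inferiority power would be 10% to 33% at a margin of 0.05, and 29% to 86% at 0.10.

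**The case against.** The strongest reply is that Section IV.G is being held to more than it says. Its closing sentence is doubly conditional. The phrase about being as good or better describes physiological information, not diagnostic accuracy alone. The hypothesis asks only for an appropriate alternative, and Section II calls the study proof-of-concept. Using the established test as the reference in a first concordance study is normal, and Section IV.G ties replacement to a close correlation, which Primary Aim 2 does estimate with an interval. The other comparisons are openly exploratory, so neither power nor a formal margin is expected.

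Much of this stands, and it rules out several stronger readings that a reader might infer:

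- *That both primary aims treat HVPG as truth.* This is literal only for Primary Aim 1. In Primary Aim 2 a correlation is symmetric; the aim falls short because association is not accuracy.
- *That no head-to-head comparison is planned.* One is: the design is paired, and Section IV.F says the tests will be compared for varices. For cirrhosis, prevalence at cutoffs is a descriptive comparison. What is absent is an inferential contrast.
- *That the plan promises superiority, or attributes it to the primary aims.* It names superiority as something the study could show, and does not say by which aim.
- *That Primary Aim 1 penalises DSI by a known amount.* Section IV.G says that with large collaterals "In terms of disease severity, HVPG would be falsely low, while HQ-SHUNT would report accurately". That remark is about disease severity. It does not say that HVPG misstates pressure, that such patients fall below 6 mmHg, or how many there are, so no bias can be calculated from it.

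The reply does not remove the point. Exploratory status is a reason to narrow Section IV.G, because these aims are the only route to its comparative conclusions.

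**Conclusion.** The concern holds as a mismatch between the comparative conclusions in Section IV.G and the analyses specified. This rests on the text alone: Primary Aim 1 cannot place DSI above HVPG, Primary Aim 2 cannot rank the two tests, and the exploratory aims stop short of an estimated difference. For cirrhosis, separate regressions and prevalence at cutoffs do not carry out the comparison of cutoffs that Section I sets. For varices, the analysis moves to data-derived cutoffs although the aim names fixed ones.

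The size is illustrative. Under the assumed AUCs, group sizes and correlations, half-widths run from about 0.06 to 0.12 for cirrhosis and 0.07 to 0.13 for varices. Equal observed c-statistics could therefore coexist with DSI being worse by an amount in that range. Neither biopsy nor EGD is required, so the true numbers could be smaller. The primary results are unaffected. The change should be made, because it alters what may be concluded and uses data already planned.

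**What to change.** 1. In Section IV.F, for cirrhosis and for varices, report the paired AUC difference (DSI minus HVPG) with a DeLong 95% confidence interval, in patients who have both tests and the reference.
2. Compare sensitivity (among reference-positives) and specificity (among reference-negatives) at the pre-stated cutoffs by McNemar's test or an equivalent paired method. The cirrhosis DSI cutoff must be reconciled first: Section I gives 16.5 and Section IV.A gives 20. Keep the Youden-cutoff results as descriptive.
3. In Section IV.G, tie the claims of being as good, superior or more accurate to these paired exploratory intervals. A claim of better needs a lower limit above 0. Similar c-statistics alone must not be read as showing that DSI is as good. If a non-inferiority margin is used, fix it before analysis and require the lower limit to exceed minus the margin.

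The cost is a few lines of analysis text and standard software output, with no new data or visits. The downside is that the intervals may be inconclusive, particularly against a narrow margin, and the permitted claim will then be more modest.
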